4.2. Sample Size and Power Considerations

In total, approximately 300 subjects who have successfully completed Study MT-1186-A02 are anticipated to be enrolled in this MT-1186-A04 study. A formal sample size calculation was not performed. However, data from 380 subjects (190 subjects per group) randomized in Study MT-1186-A02 will be included for all analyses. Hence, using MT-1186-A02 and MT-1186-A04 survival data and assuming 65% survival rate of the primary endpoint for the control group, the planned sample size of 190 subjects per group initially randomized in Study MT-1186-A02 will provide 70% power to detect a statistically significant result if the true hazard ratio between edaravone 105 mg daily (test) and edaravone 105 mg on/off regimen (control) in the primary endpoint is HR=0.775 (implying 22.5% risk reduction in the hazard due to daily treatment). This calculation of 70% power assumes a 2-sided alpha of 20% based on a rare disease condition (Hilgers RD et al., 201614) using the log-rank test and a follow-up time of up to 48 weeks in Study MT-1186-A04.

When this SAP version 1.0 was finalized and signed, for 384 subjects randomized in Study MT-1186-A02, 202 subjects who have successfully completed Study MT-1186-A02 were enrolled in this MT-1186-A04 study.

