8.3.2. Efficacy Measures

8.3.2.1. Time to 12-point decrease in ALSFRS-R or death

The primary end point in this study is the time from the randomization date in Study MT-1186-A02 to the first occurrence of at least 12-points decrease in ALSFRS-R or death, whichever happens first.

ALSFRS-R is a questionnaire used to measure the impact of ALS that is evaluated by the Investigator. The scale measures the subjects' physical function across 12 activities of daily living. The date of the evaluation along with the results will be recorded on the eCRF with respect to "4 Handwriting" and "5 eating motion," the results for the dominant hand (the hand used in daily life at the time of screening) will be recorded.

- ALSFRS-R total score for each visit will be derived from the sum of 12 items². For the item 5 "Eating disorder," either the item (a) or (b) will be selected corresponding to subjects with or without gastrostomy respectively. The maximum total score is 4 x 12=48.
- ALSFRS-R domains Score. The following subdomain will be calculated for each visit as well as the change from baseline to week 48.
 - O Bulbar function = total of items 1 to 3
 - O Limb function = total of items 4 to 9
 - o Fine motor function = total of items 4 to 6
 - O Gross motor function = total of items 7 to 9
 - o Respiratory function = total of items 10 to 12

The time to event variable will be calculated as follows:

Time to event=Event Date or Last Observed Date – Randomization Date + 1

- The time to the first occurrence of at least 12-point decrease in total ALSFRS-R score will be calculated from randomization date in MT-1186-A02 until last total ALSFRS-R score measurement available during MT-1186-A04. If the first occurrence of at least a 12-point decrease at any visit time point is observed, then the time variable will be calculated as the difference between the date that ALSFRS-R score was observed for which the above decreased occurred and the randomization date in MT-1186-A02.
- In case of death, the time variable will be calculated as the difference between death

² Refer to Appendix I of the protocol.

Mitsubishi Tanabe Pharma America, Inc.

date and the randomization date in MT-1186-A02.

• In case the subject did not experience either of the above events, the time variable will be calculated as the difference between date of the last observed date (Censored date) and the randomization date in MT-1186-A02.

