Since the MT-1186-A02 and MT-1186-A04 clinical trials will not collect information on King's Stage directly, ALSFRS-R item responses and patients' survival will be mapped to stages for every ALSFRS-R collected visit using the above published algorithm and patientlevel data. Patients with baseline ALSFRS-R assessments at MT-1186-A02 that will not meet criteria for lower limb, upper limb, or bulbar involvement, and that also will not have evidence of Stage 4A or Stage 4B, will be designated "Stage 0", as their assessments could not be mapped to the King's ALS Clinical Staging System. For the King's stage derivation, the available ALSFRS-R data at each analysis visit will be used in the subjects who were not dead. If the subject was reported as death from the last observation visit to last day of the nearest analysis visit window, the King's stage from the analysis visit will be Stage 5. If a subject not reported as death will have missing ALSFRS-R assessment at each visit, the last observation will be carried forward for the last King's stage value: In the vast majority of circumstances patients will either remain in the same clinical stage from one assessment to the next or they will experience a decline in stage. In those relatively rare instances, in which subject will be found to improve from one assessment to the next, the value from their immediately prior assessment will be used rather than the actual observed value, because the improvement will be considered to be temporary or spurious.

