9.2.2.2.3. King's ALS Clinical Stage Derived from ALSFRS-R Score and Death Event

King's ALS Clinical Stage analysis will be done using the FAS. A shift table to each visit throughout the periods of both MT-1186-A02 and MT-1186-A04 from baseline category will be summarized using number and percentages.

Mitsubishi Tanabe Pharma America, Inc.

For the Kings ALS Clinical Staging System, attention will focus on two events of clinical progression:

- Any decline in stage from baseline
- Any \geq 2-stage decline from baseline

These events will be analyzed in terms of both the proportion of patients who will experience the events between baseline and visit Week 96 (A04 Week 48) in MT-1186-A04 using chi square test for proportions, as well as the time to these events using stratified log rank test using the randomization strata of ALSFRS-R rate of decline score during the screening period (2 levels strata of -1,-2 or -3,-4), Geographical Region (3 levels strata of Europe, America or Asia Pacific). For the latter, study dropouts prior to any event will be treated as censored as of the date of their first missing assessment. The time to event will be also displayed using the Kaplan Meier figure. Comparisons will be made between treatment groups on an overall basis, as well as controlling for King's stage at baseline using Cochran–Mantel–Haenszel test (CMH).

Mitsubishi Tanabe Pharma America, Inc.

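### King's-stage dropouts are censored at their first missed assessment, which counts up to about 12 weeks without a stage reading as event-free and pushes the Kaplan-Meier curves upward

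*SAP*

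**What the plan says.** SAP 9.2.2.2.3 defines two progression events on the King's scale: "Any decline in stage from baseline" and a decline of two or more stages. It compares "the time to these events using stratified log rank test", shows Kaplan-Meier curves, and adds comparisons of proportions. For the time-to-event part it states that "study dropouts prior to any event will be treated as censored as of the date of their first missing assessment".

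SAP 8.3.2.3 explains how the stage arises. It is not collected directly. ALSFRS-R responses are "mapped to stages for every ALSFRS-R collected visit". Two further rules in that section matter here:

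- **Deaths.** "If the subject was reported as death from the last observation visit to last day of the nearest analysis visit window", the stage at that analysis visit is 5.
- **Missing visits.** For a subject not reported dead who misses an ALSFRS-R, "the last observation will be carried forward for the last King's stage value".

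The other time-to-event endpoints are censored differently. For the primary endpoint, a subject without an event is handled in SAP 8.3.2.1 as follows: "the time variable will be calculated as the difference between date of the last observed date (Censored date". SAP 8.3.2.2.3 also uses the last observed date for time to death, tracheostomy or permanent ventilation. No reason is given for a different rule for King's stage.

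**The concern.** A stage decline is dated at the visit where it is seen. A subject last assessed event-free at one visit, with no ALSFRS-R at the next, cannot contribute a non-fatal decline at that next visit. The SAP rule still leaves the subject in the denominator there. The visit hazard is then too low and the event-free curve too high. With the same events, every risk set under the SAP rule contains the corresponding risk set under last-assessment censoring. So the SAP curve can never be the lower of the two, and it is higher wherever a retained dropout shares a risk set with a later event.

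The level of both curves is at stake and, if one arm loses more subjects, so is the comparison between them. The rule is also hard to program. A missed assessment has no recorded date, and the SAP does not say whether to use the nominal day or a window edge. It does not say whether subjects who completed A02 without entering A04, or who were ongoing when the studies stopped, are dropouts. Under SAP 5.1 and 5.2 the interim analysis is the one that will be run and the final analysis will not be, so there is no later analysis in which to settle this.

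**Working it through.** **The plan's own figure.** The only survival-type figure is 70% power for the primary endpoint (190 per group, hazard ratio 0.775, 65% event-free at Week 48 in controls, two-sided alpha 20%). With exponential times over 96 weeks, expected events are 190 × [(1 − 0.65²) + (1 − 0.65^(2×0.775))] = 202.3, and Schoenfeld's formula gives 70.2%. The figure reproduces, but it says nothing about King's stage. All rates below are assumptions shown as ranges.

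**Inputs from the documents.** ALSFRS-R visits at Weeks 4, 8, 12, 24, 36, 48, 60, 72, 84 and 96 (SAP 9.2.2.1.2). 384 subjects randomized in A02, of whom "202 subjects who have successfully completed Study MT-1186-A02 were enrolled in this MT-1186-A04 study" (SAP 4.2), leaving 384 − 202 = 182, or 47.4%, who did not enter.

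**Formula.** Let *h* be the true probability of an event over a visit gap and *q* the share of the risk set that drops out in that gap. Last-assessment censoring estimates *h*. The SAP rule estimates *h*(1 − *q*), because the dropouts stay in the denominator with no chance of a stage event.

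**Central case: 65% event-free and 20% dropout by Week 48.**

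- 4-week gap: *h* = 1 − 0.65^(4/48) = 0.0353; *q* = 1 − 0.80^(4/48) = 0.0184; *h*(1 − *q*) = 0.0346.
- 12-week gap: *h* = 1 − 0.65^(12/48) = 0.1021; *q* = 1 − 0.80^(12/48) = 0.0543; *h*(1 − *q*) = 0.0966.
- Week 48 (three gaps of each length): (1 − 0.0346)³ × (1 − 0.0966)³ = 66.3%, against a true 65.0%.
- Week 96 (four more 12-week gaps): 44.2%, against 0.65² = 42.25%.

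**Range.** Overstatement in points, for true Week 48 event-free rates of 20% to 80%:

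| Dropout by Week 48 | Week 48 | Week 96 |
|---|---|---|
| 10% | 0.4 to 0.9 | 0.4 to 0.9 |
| 20% | 0.8 to 1.9 | 0.9 to 1.9 |
| 30% | 1.3 to 3.1 | 1.4 to 3.1 |
| 40% | 1.9 to 4.4 | 2.1 to 4.5 |

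**Week 60, if non-entrants count as dropouts.** Suppose first that all 182 were assessed event-free at the same rate as entrants at Week 48, with no other dropout. The Week 48 to 60 hazard is then multiplied by 202/384 = 0.526:

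| Median time to decline | SAP rule | True | Gap |
|---|---|---|---|
| 40 weeks | 0.435 × (1 − 0.188 × 0.526) = 39% | 35% | 3.9 |
| 60 weeks | 0.574 × (1 − 0.129 × 0.526) = 54% | 50% | 3.5 |
| 90 weeks | 0.691 × (1 − 0.088 × 0.526) = 66% | 63% | 2.9 |

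Adding 20% ordinary dropout by Week 48, the gap is 4.6 points at 65% event-free and 5.8 points at 35%. If only 10% fail to enter, it is 2.2 points at 65% event-free with the same ordinary dropout, and 0.6 to 0.8 points without it (medians of 90 to 40 weeks).

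**Comparison of arms** (simulation, 190 per arm, 3,000 runs, unstratified log-rank, 65% event-free at Week 48 in controls; median estimated hazard ratio, and rejection at 5%):

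| True HR | Dropout daily / on-off | Last assessment | SAP rule |
|---|---|---|---|
| 1 | 20% / 20% | 1.008; 4.9% | 1.009; 4.8% |
| 0.775 | 20% / 20% | 0.766; 37.3% | 0.766; 37.1% |
| 1 | 10% / 30% | 0.998; 5.2% | 1.059; 6.3% |
| 1 | 30% / 10% | 0.998; 4.8% | 0.942; 6.0% |
| 0.775 | 10% / 30% | 0.757; 37.8% | 0.804; 24.7% |

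**Deaths after dropout.** If a share of events are deaths still ascertained after dropout, the Week 48 estimates in the central case (true value 65.0%) are:

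| Share of events that are captured deaths | SAP rule | Last assessment, later deaths still counted |
|---|---|---|
| 0% | 66.3% | 65.0% |
| 30% | 65.9% | 64.6% |
| 50% | 65.7% | 64.4% |
| 100% | 65.0% | 63.7% |

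**The case against.** The strongest reply has four parts.

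1. **Deaths and early-termination visits are observed.** A reader might infer that a retained dropout can have no event at all in the added interval. The documents do not support that. SAP 8.3.2.3 maps a death to Stage 5, Protocol 8.1 and 9.6 require phone follow-up after discontinuation, and an ALSFRS-R is scheduled at the ET visit. This stands: the unobserved part is non-fatal decline after the last ALSFRS-R. It also limits the fix. Censoring at the last ALSFRS-R while still counting every later death errs the other way, and if about half of the events were such deaths it would do no better than the present rule.

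2. **The 47% is not a dropout rate.** A reader might infer that the risk set nearly doubles between Weeks 48 and 60. SAP 4.2 says only how many subjects enrolled. The other 182 may include deaths, early A02 terminations, ineligible subjects and subjects still in A02 when it stopped. A completer who did not enrol has no Week 60 visit to miss. SAP 4.1, 5.1 and 5.2 also show that follow-up ended early, so full follow-up to Week 96 does not describe this dataset. This stands: the Week 60 figures are a ceiling on the effect of non-entry.

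3. **The log-rank test need not be distorted.** This stands when dropout is equal between arms. The documents give no dropout by arm.

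4. **The endpoint is exploratory.** There is no type I error correction, and shift tables and comparisons of proportions stand beside it. This stands and limits the importance of the point.

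The carry-forward rule is no defence. It can be read as serving the visit tables only, since the assessment is still missing when a stage is carried forward. The SAP does not say so, and read literally a living dropout never has a missing stage.

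**Conclusion.** The concern holds in limited form. The rule biases the King's-stage event-free curves upward, and the direction needs no assumed rates as long as the same events are counted under both rules. The size does need them: 0.4 to 4.5 points over the range tried, 1 to 2 points in the central case, and about 3 to 5 points at Week 60 (5.8 in the faster-progression case) if every non-entrant is counted as a dropout, which is an upper bound on that share. These figures assume exponential times, dropout unrelated to progression, and no deaths captured after dropout; captured deaths shrink the bias. The treatment comparison is materially affected only if dropout differs between arms. No primary or secondary result depends on this rule. It merits correction because the change is cheap, the rule departs without explanation from the SAP's other endpoints, and the present wording lets two programmers produce different curves.

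**What to change.** Replace the censoring sentence in SAP 9.2.2.2.3 with:

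> Subjects without a stage-decline event are censored at the date of their last non-missing ALSFRS-R assessment (including the ET assessment). This also applies to subjects who did not enter A04 and to those ongoing at study termination. The carry-forward in 8.3.2.3 is not used to extend time at risk.

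Add one consistent rule for deaths after the last ALSFRS-R. For example, count a death as an event only if it falls within a pre-stated window after the last assessment, with a sensitivity analysis that counts all deaths. A shorter window leaves less of the opposite bias shown above.

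The cost is one or two sentences for the censoring rule, one for deaths, and slightly less follow-up time. No new data are needed, because ALSFRS-R evaluation dates are already recorded (Protocol 12.1.1). The change does not remove the assumption that dropout is unrelated to progression, so the number censored by arm and visit should be shown beside the curves.

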9.3. Safety Analysis

Safety assessments will be made on the SAF and data from MT-1186-A02 and MT-1186-A04 will be descriptively summarized and safety data from MT-1186-A04 only will be listed.

9.3.1. Adverse Events

The following summaries will be provided:

A Summary table by treatment group of the overall incidence (number and percentage)
and the number of events will be provided for TEAE, TEAE related to study drug, severe
TEAEs, TESAEs, TEAEs leading to study treatment discontinuation and TEAEs leading
to death.

The numbers and proportions of subjects will be calculated for the following:

- TEAEs by SOC and PT
- TEAEs by SOC, PT and severity
- Severe TEAEs by SOC, PT
- Most Common (>=5% of patients) TEAEs by SOC and PT
- TEAEs related to study drug by SOC and PT
- TEAEs related to study drug by SOC, PT and severity
- TESAEs by SOC and PT
- TESAEs related to study drug by SOC and PT
- Severe TEAEs by SOC and PT
- Severe TEAEs related to study drug by SOC and PT
- TEAEs leading to study treatment discontinuation by SOC and PT
- Study drug-related TEAEs leading to study treatment discontinuation by SOC and PT
- TEAEs by SOC, PT and relationship to study drug
- TESAEs by SOC, PT and relationship to study drug
- TEAEs leading to death by SOC and PT
- Study drug-related TEAEs leading to death by SOC and PT

The following summaries will be provided:

 A Summary table of the overall incidence (number and percentage) will be provided for Peripheral Neuropathy Standardized MedDRA Query (SMQ) TEAEs

The numbers and proportions of subjects will be calculated for the following:

- TEAEs of Peripheral Neuropathy Standardized MedDRA query (SMQ) by SOC and PT
- TESAEs of Peripheral Neuropathy SMQ by SOC and PT
- COVID-19 TEAEs by SOC and PT

Mitsubishi Tanabe Pharma America, Inc.

For each of the summaries, multiple occurrences of the same event within a subject will be counted once in the summaries by SOC and PT; multiple occurrences of the same event within a subject will be counted once in the maximum severity category (severe > moderate > mild) and/or maximum study drug relationship category (reasonable possibility / no reasonable possibility). If severity or relationship is found to be missing the most severe occurrence will be imputed for that particular summary.

TEAEs by Oral/PEG subgroup, SOC and PT

The numbers and proportions of subjects with TEAEs and event rate of TEAEs will be calculated by Oral/PEG subgroup, SOC and PT. The event rate of TEAEs will be calculated as the number of TEAEs divided by total exposure to investigational product by Oral/PEG dosing and expressed as 100 person years. Any TEAE that occurred after subject switched to PEG will be classified under the PEG subgroup. The exposure (in days) under Oral until switched to PEG will be calculated as difference: Oral days=PEG switch Date - Date of first study drug in MT-1186-A02. The exposure under PEG will be calculated as difference: PEG days= Date of last study drug - PEG switch Date.

Subject's data listings will be provided for: TEAEs, TEAE leading to discontinuation of study drug and TEAE leading to Death.

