15 ADVERSE EVENT MANAGEMENT

All AEs and SAEs will be recorded in the source documents. All AEs and SAEs that occur from the time written ICF is obtained until the end of the Safety Follow-up Period will be recorded in the eCRF. Even if an AE is assessed by the Investigator as not related to IMP, its occurrence must be recorded in the source documents and eCRF. AEs will be classified as 'treatment-emergent' if they arise following the administration of IMP or if a pre-dose AE increases in severity following dosing.

At each study visit, after the subject has had an opportunity to spontaneously mention any problems, the Investigator should inquire about the occurrence of AEs. The questioning should be open-ended and non-leading.

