8.3.1.4. Exposure to Study Medication and Compliance

Exposure

The actual duration of exposure in days will be calculated from the first study drug in MT-1186-A02 as follows

Exposure duration (days)=Date of last study drug – date of first study drug in MT-1186-A02 + 1

If the date of first study drug dose or the date of the last study drug dose cannot be determined, then the duration calculation will not be completed. Interruptions and compliance will not be considered for the duration of exposure.

Page 23 of 61

Confidential

Mitsubishi Tanabe Pharma America, Inc.

The total exposure in person years will be calculated as the sum of duration of exposure to study treatment over all patients in days divided by 365.25.

Treatment Compliance

Treatment compliance will be calculated for each subject using the following:

Treatment compliance(%)

 $Exposure \ duration - count \ of \ study \ medication \ days \ missed + \\ = \frac{count \ of \ additional \ study \ medication}{Exposure \ duration}$

 $\times 100\%$

The #count of study medication missed and additional study medication are collected by CRF visit.

Treatment compliance will be calculated using the formula above and reported to 1dp.

Date switched to PEG/RIG administration

If the date of switched to PEG/RIG administration is partial, then it will be imputed as follows:

- If the switched day is missing, the first day of the month will be used.
- If the switched day and month are missing, then the first day of the first month (January) will be used.

If the imputation date is earlier than date of the first study drug, the imputation date will be same as date of the first study drug.

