8.3.3. Safety Measures

8.3.3.1. Adverse Events

An AE is any untoward medical occurrence in a subject or clinical investigation subject administered a pharmaceutical product that does not necessarily have a causal relationship with this IMP. An AE can therefore be any unfavorable and unintended sign (including an abnormal laboratory finding, for example), symptom, or disease temporally associated with the use of an IMP, whether or not considered related to the IMP.

Adverse events will be coded according to the MedDRA version 23.0

- Adverse Events will be classified for Treatment Emergent AEs (TEAEs) if at least one of the following conditions is met:
 - The AE was not present before the first dose in Study MT-1186-A02 but started after administration of the first dose of study drug in Study MT-1186-A02, or,
 - The AE was present before the first dose in Study MT-1186-A02 but increased in severity following administration of the first dose of study drug in Study MT-1186-A02.

Mitsubishi Tanabe Pharma America, Inc.

Integration of continued AEs from MT-1186-A02 to MT-1186-A04:

TEAE's from MT-1186-A02 will be integrated into TEAE's from the current MT-1186-A04 study in order to be able to analyze the continued safety profile. If AE in MT-1186-A04 met all following conditions, the AE in MT-1186-A02 and MT-1186-A04 will be merged into a single AE.

- Onset date of AE in MT-1186-A02 = Onset date of AE in MT-1186-A04
- Lowest level terms (LLT) of AE in MT-1186-A02 = LLT of AE in MT-1186-A04
- "Was this event ongoing at the end of MT-1186-A02?" in MT-1186-A04 CRF = "Yes" Then, for AE analysis, AE End date and Outcome data in MT-1186-A04 CRF data rather than MT-1186-A02 CRF data will be prioritized and analyzed.

Handling Partial Dates:

The handling of partial dates in study MT-1186-A02 were provided in a designated SAP for this study. The following are the rules for partial dates handling for TEAE's newly captured in MT-1186-A04 study:

- AE with a missing start time, but with a start date equal to the date of first dose of study treatment in MT-1186-A04 will be considered treatment-emergent.
- If the AE start date is incomplete, it will be imputed as follows for the purpose of determining TEAE:

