- Time to AE occurrence = AE start date The first administration date of study drug in MT-1186-A02 + 1.

Definition of Oral subgroup and PEG subgroup

Subjects are starting with oral administration while opting to switch from oral administration to PEG/RIG dosing based the patient's disease progresses. Therefore, if subject switched from oral dosing to PEG/RIG then the subject will be classified to the PEG subgroup. Otherwise, the subjects will be classified as Oral subgroup.

Mitsubishi Tanabe Pharma America, Inc.

Definition of TEAE under Oral dosing and PEG dosing

If the subjects have the date subject switched to PEG/RIG dosing, TEAEs after the switched date will be defined as TEAEs under PEG dosing. Otherwise TEAEs will be defined as TEAEs under Oral dosing.

- If switch date is incomplete, it will be imputed as follows for the purpose of determining PEG duration:
 - o If the switch day is missing, but the month and year are not missing, then the 15th will be used.

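### The Oral and PEG/RIG adverse-event rates count events beyond the last dose but stop person-time at the last dose, which probably inflates the PEG rate more than the Oral rate

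*SAP*

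**What the plan says.** SAP 9.3.1 (TEAEs by Oral/PEG subgroup) defines the rate as "the number of TEAEs divided by total exposure to investigational product by Oral/PEG dosing", expressed per 100 person-years. For a subject who switches, the oral part is "Oral days=PEG switch Date - Date of first study drug in MT-1186-A02", and for the other part "The exposure under PEG will be calculated as difference: PEG days= Date of last study drug - PEG switch Date". The PEG numerator is open-ended: "Any TEAE that occurred after subject switched to PEG will be classified under the PEG subgroup". No oral formula is given for a subject who never switches.

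Three other places bear on this:

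- SAP 8.3.3.1 splits events at the switch date: "TEAEs after the switched date will be defined as TEAEs under PEG dosing. Otherwise TEAEs will be defined as TEAEs under Oral dosing". It also defines a TEAE by its start only ("The AE was not present before the first dose in Study MT-1186-A02 but started after administration of the first dose of study drug", or a worsening after that dose), with no cut-off after the last dose.
- SAP 8.3.1.4 defines a subject's exposure as "Date of last study drug – date of first study drug in MT-1186-A02 + 1", which counts both end days.
- Protocol section 15: "All AEs and SAEs that occur from the time written ICF is obtained until the end of the Safety Follow-up Period will be recorded". Protocol 15.6 adds withdrawal from the study as an earlier end. The safety follow-up lasts two weeks (SAP 4.1), with a call at Week 50, plus or minus 7 days (Protocol 10.1.4).

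**The concern.** A rate per person-year is interpretable only if events are counted over the same days that make up the denominator. Here they are not. An event with onset in the two weeks after the last dose is a TEAE and is assigned to a route, but those days appear in neither route's person-time.

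The mismatch affects both routes, though probably not equally. A switcher contributes oral days that end at the switch and so have no tail. The switcher's whole tail goes to PEG, where the denominator is only the time after the switch. The shorter that time, the larger the relative effect.

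Among the AE summaries listed in SAP 9.3.1 this is the only one divided by exposure, and it sets PEG/RIG dosing beside oral dosing. A difference of several percent created by the formulas could be taken for an effect of the route. A second, smaller point is that the two parts of a switcher's exposure do not add up to that subject's exposure elsewhere in the SAP.

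**Working it through.** The documents give no rate, PEG exposure or number of switchers, so there is no figure of the plan's own to reproduce. The check applies day counts to the stated formulas.

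**Notation.** First dose on day *f*, switch on day *s*, last dose on day *l*. Total exposure T = l - f + 1 (SAP 8.3.1.4). Oral days O = s - f and PEG days P = l - s (SAP 9.3.1).

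**Step 1: the one-day gap.** O + P = l - f = T - 1. With f = 1, s = 337, l = 673: O = 336, P = 336, sum 672, against T = 673.

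Which route loses the day depends on who owns the switch day. Under SAP 8.3.3.1 only events after the switch date are PEG. On-drug PEG event days are then s + 1 to l, that is l - s = 336, equal to PEG person-time. On-drug Oral event days are f to s, that is 337, against 336 person-days. The uncounted day is the switch day, and it belongs to Oral.

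**Step 2: the post-dose tail.** Let *k* be the days of AE recording after the last dose and *p* the share of switchers. Assume the same constant true event rate on both routes and in the tail, with common T and P across subjects. For never-switchers, take T as the oral person-time. With the switch day in Oral, event days divided by person-days are:

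- PEG: (P + k) / P
- Oral: [p(O + 1) + (1 - p)(T + k)] / [pO + (1 - p)T]

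Example with P = 84, k = 14, T = 673, p = 0.1, so O = 588:

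- PEG: 98/84 = 1.167
- Oral: (58.9 + 618.3)/(58.8 + 605.7) = 677.2/664.5 = 1.019
- Spurious ratio: 1.167/1.019 = 1.145

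**Step 3: range with a 14-day tail for all.** T = 337 or 673, p = 0.1 or 0.3. The ratio range covers both readings of the switch day.

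| PEG days | PEG factor, switch day in Oral | PEG factor, switch day in PEG | PEG/Oral ratio |
|---|---|---|---|
| 84 | 98/84 = 1.167 | 99/84 = 1.179 | 1.12-1.16 |
| 168 | 182/168 = 1.083 | 183/168 = 1.089 | 1.04-1.07 |
| 336 | 350/336 = 1.042 | 351/336 = 1.045 | 1.00-1.03 |

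The Oral factor in these cases is 1.015 to 1.043, so Oral is inflated too. With a tail of 7 or 21 days (the visit window), the ratio at 84 PEG days is 1.06-1.09 or 1.18-1.23.

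**Step 4: can the direction reverse?** Give switchers no tail, never-switchers 14 days, and p = 0.2. With T = 337 and P = 308 (O = 28), the PEG factor is 1 and the Oral factor is (5.8 + 280.8)/(5.6 + 269.6) = 286.6/275.2 = 1.041, so the ratio is 0.960. Across the no-tail cases tried it was 0.96 to 0.985.

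**The case against.** The strongest objection concerns the tail itself. The Week 50 call is for subjects who complete treatment (Protocol 10.1.4), and AE recording otherwise ends at withdrawal (Protocol 15.6). Subjects who need tracheostomy or permanent ventilation are withdrawn (Protocol 9.6), and switching follows disease progression (SAP 8.3.3.1). Switchers may therefore have less post-dose recording than others. This stands as a limit on the direction of the bias but does not remove the mismatch. If the study is terminated, as SAP 4.1 reports, Protocol 18.6 asks for follow-up assessments in all subjects. Against that, SAP 5.1 limits the analysis to data up to the cessation of Study MT-1186-A02, and post-dose follow-up of subjects who never entered A04 is not described in these documents. A uniform 14-day tail is an assumption.

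The second objection is about weight. The table is descriptive, has no test, and compares groups formed after randomization by disease progression. A raw PEG/Oral contrast is confounded by disease stage in any case. That is fair, and it keeps the point small.

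A reader might also infer three stronger things that the documents do not support:

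- *That PEG time omits a day and needs a + 1.* Under SAP 8.3.3.1, PEG person-time already matches PEG event days on drug. Adding a day to PEG alone would put the switch day in PEG person-time while its events stay in Oral.
- *That only PEG is affected.* Never-switchers' events after the last dose are Oral events, and their exposure also stops at the last dose.
- *That the formulas always give a higher PEG rate.* Step 4 shows they need not.

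**Conclusion.** The event window and the person-time do not match on either route, and this follows directly from the SAP text. The PEG rate is probably inflated more than the Oral rate, by about 12-16% at 84 PEG days, 4-7% at 168 and 0-3% at 336. These figures assume equal true rates, a tail of 14 days for everyone, 10-30% switchers and total exposure of 337 or 673 days. None of the PEG durations or switch counts is in the documents, and the sign reverses if switchers have little or no post-dose recording.

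The one-day shortfall is certain but minor. It lies in Oral if SAP 8.3.3.1 governs; SAP 9.3.1 read alone leaves the switch day open. No efficacy result, treatment-group comparison or incidence table depends on either point. The change is worth making because it is cheap and removes a bias from a stated rate.

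**What to change.** In SAP 9.3.1, for both routes and explicitly including never-switchers, use one end date for the numerator and the person-time. Either:

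1. count in these rates only TEAEs with onset on or before the last dose date; or
2. extend person-time to the last day on which AEs were collected for that subject.

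Assign the switch day to one route in both SAP 8.3.3.1 and SAP 9.3.1. If the 8.3.3.1 rule is kept, Oral days = switch - first + 1 and PEG days = last - switch, which sum to the exposure in SAP 8.3.1.4. For a never-switcher, Oral days = last - first + 1. Under option 2 the last day of AE collection replaces the last dose date in the PEG formula and in the never-switcher formula.

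The same edit should reconcile the imputation of a partial switch date with a missing day. SAP 8.3.1.4 uses the first of the month and SAP 8.3.3.1 the 15th, which can move the split by 14 days.

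The cost is a few lines of derivation text and programming. With option 1, post-treatment events appear in the incidence tables but not in this rate, which needs a footnote. With option 2, the rate is no longer strictly per time on drug.
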